Specific Aim 2: To characterize inflammatory mechanisms contributing to the inter-individual variability in analgesic response to OT. We will assess central and peripheral inflammatory processes using proton MRS in frontal brain regions and plasma immune markers, respectively. Based on our preliminary data, we hypothesize that compared to P, OT administration will result in significant: **H2a**) decrease in plasma levels of IL-6, TNF- α , and IL-10; and **H2b**) decrease in brain metabolite concentrations associated with inflammation (i.e., *MI*, Cr, Cho). Further, **H2c**) decrease in brain metabolites and systemic cytokines will be significantly associated with decrease in clinical pain intensity. Other markers of brain structure and function will also be significantly associated with changes in clinical pain intensity (**H2d**).

Exploratory Aim 3: To characterize effects of acute intranasal OT administration on clinical and experimental pain as well as underlying neurobiological mechanisms in younger and older controls. We will perform similar experiments as above in control participants to further understand OT's analgesic effects across the lifespan in the absence of knee OA pain. However, acute OT administration will be used in healthy controls versus chronic administration in the presence of Knee OA.

6. Research Plan

We propose a double-blinded, randomized cross-over design that will randomize older adults with symptomatic knee OA pain and/or back pain to four weeks of intranasal self-administration of either OT or P (48 IUs daily) followed by a four-week washout period and a second four weeks of intervention (either OT or P). Our study design was guided by recommendations by the IMMPACT group for clinical pain trials.⁷⁴⁻⁷⁷ After initial screening, eligible participants will undergo up to four baseline sessions (health, sensory, and neuroimaging) for collection of clinical, functional (physical, cognitive, emotional), QST, and brain imaging data lasting 2-3 hours. At some point during the baseline, intervention, and post-intervention periods, participants may wear a Samsung Gear S[®] or Apple smartwatch or Oura ring to obtain daily pain, mood, and social activity assessments and to objectively measure physical activity levels and sleep quality. During the intervention, participants will self-administer twice daily 24 IUs

Protocol: IRB201801467 (UCOPE Study)

IRB version: 10/1/2018

PI version: 05/10/2024

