Neuroimaging (up to 2 visits each time). Participants will lay supine in the MRI magnet for up to 2 hours and fill out a post event questionnaire at the conclusion of the scan. We will use a state-of-the-art 3T Siemens Prisma MR system at the McKnight Brain Institute (MBI) for collecting anatomical, structural, functional, and biochemical scans. Anatomical image acquisition will involve a T1-weighted structural scan using a magnetization-prepared rapid gradient echo (MPRAGE) sequence, and a T2 FLAIR scan, which provides good contrast between gray and white matter, and cerebrospinal fluid based on tissue T1 and T2 differences. Functional scans (fMRI) will be taken while the participant is resting quietly, completing a cognitive task and while painful stimulation is being applied using a (MRI-compatible) heat thermode routinely used in neurological examinations. We will also acquire single-voxel MEGA-PRESS water-suppressed ¹H spectra with water T2 measurement. A simple visual task will also be performed to control for non-specific cognitive influences. Brain MRI data will be used to measure the structural and functional integrity of the brain including, but not limited to, descending sensory and motor tract integrity (fiber tractography), intracranial volume, whole brain volume, lacunae as well as metabolite concentrations.

fMRI data analysis. We will use the same stages for functional connectivity analysis as prior work^{12,13} using Freesurfer (<http://surfer.nmr.mgh.harvard.edu/>) and AFNI (<http://afni.nimh.nih.gov/afni/>). Seed regions will be placed in areas that include prefrontal, striatal and insular regions. To calculate the time series of the region of interest (ROI), a sphere with a radius of 3.5mm will be placed in the structure of interest (based on an MNI template). An inverse transform derived from the anatomical scan will be applied to transform the ROI from MNI common space into subject space. The mean signal of non-zero voxels within the ROI will be calculated. Pearson correlation maps will be created by correlating time series in a seed region to residual time series in each voxel of the brain. The maps are then converted to a z-score via a Fisher tanh-1 transform in order to perform a group analysis and z-score maps are transformed into MNI space via transforms derived from warping the anatomical scans.

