Magnetic Resonance Spectroscopy (MRS): A non-invasive, non-ionizing radiation technique that uses proton signals to determine the relative concentrations of target brain metabolites. The GABA-edited spectra will be acquired using a MEGA-PRESS sequence, TE 68ms; TR 2s; 14ms sinc-Gaussian editing pulses applied at 1.9 ppm (ON) and 7.56 (OFF); VAPOR water suppression; 10 min duration). Spectra will be analyzed using the Gannet package for the batch analysis of GABA-edited MR spectra, quantifying GABA concentration relative to water, correcting for voxel CSF fraction. OFF spectra will be analyzed using LCModel to give concentrations for additional metabolites NAA, Glx, Cho, MI, and Cr. Assurance: GABA-edited MR spectra will be visually screened, and spectra with a fitting residual of over 10% will be accepted for further analysis. The concentration measures for the additional metabolites will be accepted with an LCModel Cramer-Rao lower bounds (%SD) of less than 20%, a reliable estimate for a given metabolite for group comparisons.

In general, questionnaires and testing may be collected during any session that is most convenient for the participants as long as all the data is collected before randomization to intervention. Participants will also be allowed to complete any of the assessments during extra visits to reduce their burden and avoid participant fatigue. All sessions will begin with an intake interview regarding events that occurred during the past 24 hours.

Intervention period for Knee OA Participants

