where y_{ik} is the outcome variable (e.g., pain intensity/sensitivity/function for Aim 1) for subject i and visit k ($k = 1$ for intervention and $k = 2$ for post-intervention); μ is the intercept term; $\alpha_i \sim N(0, \sigma_0^2)$ is the random effect with variance term σ_0^2 for subject i ; z_i is the treatment indicator with $z_i = 0$ for P and $z_i = 1$ for OT, β is the treatment effect (OT effect compared to P effect) and $\mathbb{I}(\cdot)$ is the indicator function which equals 1 if the argument inside (\cdot) is true and equals 0 otherwise; x_{il} is the l^{th} covariates for subject i with $l = 0$ for baseline level (e.g. baseline pain intensity before treatment for Aim 1) and $l = 1, 2, \dots, L$ for L covariates (i.e., age, sex, race...); η is the time effect of post-intervention visit compared to pre-intervention visit; θ is the interaction effect between post-intervention and OT; $\varepsilon_{ik} \sim N(0, \sigma^2)$ is the error term with variance σ^2 . From equation [1], we will test whether there is a significant OT effect for both intervention and post-intervention. LMEMs allow for missing data if missing-at-random (MAR).

Table 3. Proposed hypotheses and planned analyses.

Specific Aims	Hypotheses	Planned Analyses
#1: Clinical and experimental pain	H1a: OT vs. P administration will reduce self-reported pain intensity	LMEMs* ; DV: Clinical pain IV: Treatment (OT/P)
	H1b: OT vs. P administration will decrease experimental pain sensitivity	LMEMs* ; DV: QST IV: Treatment (OT/P)
	H1c-1e: OT vs. P administration will increase physical, cognitive and emotional function	LMEMs* ; DV: SPPB, Exe. Function, Catastrophizing IV: Treatment (OT/P)
#2: Inflammatory mechanisms	H2a: OT vs. P will decrease systemic inflammation	LMEMs* ; DV: Plasma cytokines (IL6, TNF α , IL10) IV: Treatment (OT/P)
	H2b: OT vs. P will decrease brain metabolite concentrations associated with neuroinflammation	LMEMs* ; DV: Brain metabolites (tCr, MI, Cho) IV: Treatment (OT/P)
	H2c: Decrease in brain metabolites and systemic cytokines will be associated with decrease in clinical pain	Correlations/ Regressions IV: Decrease in brain metabolites and systemic cytokines DV: Decrease in clinical pain

Note. **IV** = Independent variable; **DV** = Dependent variable; **LMEMs**: linear mixed effects models; *Adjusted for baseline outcomes and covariates (age, sex, race, BMI, KL score, hip OA, plasma biomarkers).

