For **Aim 1**, the primary outcome will be self-reported pain, and plasma levels of OT as a modifier of a significant treatment (OT vs. P) response, using an intent-to-treat approach. Secondary outcomes include a standardized, multimodal experimental pain battery and physical, cognitive, and emotional functioning measures. For hypotheses **H1a** to **H1e**, we will use equation [1] to evaluate and test the effect of OT at 4-weeks post-intervention compared to P. Baseline outcomes and covariates (age, sex, race, hip OA, and inflammatory biomarkers) will be properly adjusted. A 50% reduction in self-reported pain intensity will demonstrate a clinically significant effect of OT compared to P. For **Aim 2**, the primary outcomes are proton MRS metabolites in frontal brain regions (tCr, MI, Cho) and plasma immune markers (IL-6, TNF- α , IL-10). For hypotheses **H2a** and **H2b**, we will use equation (1) to evaluate changes from baseline to post-intervention. Covariates (age, sex, race, hip OA) will be properly adjusted. For hypothesis **H2c**, we will use correlational tests and regression methods to evaluate the association between brain metabolites, systemic cytokines, and clinical pain to consider the inter-individual variability in treatment response. Consistent with IMMPACT recommendations we will perform a secondary analysis considering total number and amount of rescue medication doses in a matrix alongside pain relief, with higher scores assigned to those patients with high levels of relief and minimum rescue, and lower scores assigned to patients who have rescued the most and have lower pain relief scores.⁷⁷ For exploratory aim 3, similar strategies will be employed.

7. Possible Discomforts and Risks

Equipment used in this research meet all current safety standards, and all research staff will be highly trained in the use of all equipment. This study may include risks that are unknown at this time. Potential risks for this study are related to use of study product, neuroimaging, blood draw procedure, blood pressure measurement, the physical performance tests, the cognitive function tests, the sensory testing, and potential loss of confidentiality related to study participation, as discussed in detail below.

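### The acceptance rule for GABA spectra is worded backwards: it admits fits with a residual over 10%, where a larger residual means a worse fit (minor wording correction)

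*Combined protocol and SAP*

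**What the plan says.** Section 6 (Research Plan) of the UCOPE protocol, in the Magnetic Resonance Spectroscopy paragraph, describes two streams of spectroscopy data from the edited acquisition.

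- **GABA.** The edited spectra are processed in the Gannet package, and GABA is expressed relative to water. The quality rule is: "GABA-edited MR spectra will be visually screened, and spectra with a fitting residual of over 10% will be accepted for further analysis".
- **Other metabolites.** "OFF spectra will be analyzed using LCModel to give concentrations for additional metabolites NAA, Glx, Cho, MI, and Cr". Their quality rule follows directly: the concentrations "will be accepted with an LCModel Cramer-Rao lower bounds (%SD) of less than 20" per cent.

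The statistical parts of the plan name only metabolites from the second stream. The H2b row of Table 3 has "DV: Brain metabolites (tCr, MI, Cho"), and the data-analytic strategy says of Aim 2 that "the primary outcomes are proton MRS metabolites in frontal brain regions (tCr, MI, Cho"), together with the plasma immune markers.

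**The concern.** A quality-control rule should keep the spectra that the model describes well and drop those that it describes badly. The GABA rule as written does the reverse: exceeding 10% is the stated ground for acceptance. It is also the only numeric acceptance rule for GABA in the documents, so an analyst has nothing else to turn to.

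What is at stake is the make-up of the GABA dataset. An analyst who follows the sentence literally keeps the wrong spectra, or applies no residual limit at all. An analyst who silently reverses it departs from the written plan, and privately decides both the cut-off and what to do at the boundary. Neither is a good position once the data are in hand.

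**Working it through.** The plan gives no figure to reproduce. The check consists of reading the rule, comparing it with its neighbour, and tracing where GABA could be used.

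**1. Direction of the measure.** Let r be the fitting residual. On the ordinary meaning of the term, r is what the model fails to explain, so larger r means a worse fit. The documents do not say how r is scaled. The direction does not depend on the scaling.

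**2. The two rules side by side.**

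| Data | Measure | Accepted when | Direction |
|---|---|---|---|
| GABA-edited spectra (Gannet) | fitting residual | over 10% | larger is accepted |
| OFF spectra (LCModel) | Cramer-Rao lower bound, %SD | less than 20% | smaller is accepted |

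Both measures grow as the estimate gets worse, yet the two rules point in opposite directions.

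**3. The two possible readings of the GABA sentence.**

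- *Only* spectra over 10% are accepted. The accepted set is {r > 10%}. A spectrum with r = 15% enters. One with r = 5% has no stated route in. (Both values are illustrations.) The corrected rule accepts {r ≤ 10%}, and the two sets have no member in common, whatever the distribution of r.
- Spectra at or below 10% are *also* kept. The accepted set is {r > 10%} together with {r ≤ 10%}, which is every value of r. The threshold then excludes nothing.

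Under both readings, the number of spectra rejected for r > 10% is 0. Only visual screening could remove a spectrum, and no criteria are given for it.

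**4. Is it corrected elsewhere?** GABA is mentioned four times in the documents, all in this one paragraph. No other section restates or amends the rule, and the PANDA ancillary protocol has no spectroscopy quality rule.

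**5. Where GABA could enter an analysis.**

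- It is not named in any hypothesis in Section 5, in Table 3, or among the Aim 2 primary outcomes.
- The Neuroimaging paragraph lists, among the uses of the brain MRI data, "intracranial volume, whole brain volume, lacunae as well as metabolite concentrations", without naming GABA.
- H2d in Section 5 predicts that "Other markers of brain structure and function will also be significantly associated with changes in clinical pain intensity". GABA could be one of these markers, but is not listed.
- For the controls, who have the same imaging, the data-analytic strategy says only: "For exploratory aim 3, similar strategies will be employed".

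**6. Scans covered by the rule (its scope, not its effect).** For knee OA participants, imaging is before and after treatment in each of two phases, so at most 2 × 2 = 4 time points. The Compensation section makes the MRI portion optional. Controls have 2 scans if they take the spray and 1 if they decline it.

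**7. Where the slip may lie.** Replacing over by under gives acceptance for r < 10%. Replacing accepted by rejected gives acceptance for r ≤ 10%. The two corrections differ only at r = 10% exactly.

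**The case against.** The strongest reply is that this is copy-editing. No named result depends on GABA, and an experienced spectroscopy analyst would be unlikely to keep only the badly fitted spectra. The sentence does not contain the word only, so it can be read as merely lacking an upper limit, with visual screening still in place. The Cramer-Rao bound and the fitting residual are different measures, from different software and different spectra, so opposite directions are not in themselves a contradiction. Finally, the observation that the accepted and corrected sets do not overlap follows from their definitions and says nothing about how many scans are affected.

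Much of this stands. The point is minor, the set comparison describes the rule and not its effect, and the neighbouring rule is supporting evidence only. The error rests on the meaning of a residual. The claim about use should also be kept narrow: the plan does say that the edited spectra will be processed and carried forward, but no hypothesis or statistical model names GABA.

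None of it removes the error. The looser reading still leaves a threshold that excludes nothing, and relying on the analyst to reverse the sentence means relying on an unwritten rule.

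**Conclusion.** The rule is wrong as written, and the point is minor. The direction is clear with high confidence, and rests only on the ordinary meaning of a fitting residual. That confidence does not extend to any effect on results. The effect cannot be quantified, because the documents give neither a distribution of residuals nor a model for GABA.

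The reach is limited to GABA, and so to whatever use is made of it under H2d or exploratory Aim 3. The Aim 2 primary metabolites (tCr, MI, Cho) come from the OFF spectra under a separate rule that points the right way, and they are unaffected. So are self-reported pain, sample size, power and the significance level. Whether 10% is the intended cut-off cannot be established from the documents.

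**What to change.** Before analysis, amend the sentence so that GABA-edited spectra with a fitting residual over 10% are rejected and the remainder are accepted subject to visual screening. The sponsor should confirm that 10% is the intended cut-off and state how a residual of exactly 10% is treated.

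The cost is one sentence. Some poorly fitted scans may be lost. If the residuals are all within the limit, or if staff already apply the rule in the usual direction, nothing is lost. No change to the design, the sample size or what participants do is needed.

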We will compensate control participants with up to \$330 upon study completion in the form of a pre-paid, reloadable VISA card issued by the University of Florida or by cash payments. In particular, for completion of

- Screening Visit, Baseline Visit: \$75
- Sensory Visit: \$75
- Neuroimaging Visits (up to 2 visits): \$75 per visit
- (Optional) extra \$30 if you choose to participate in the nasal spray treatment.

Power and sample size considerations: Based on our pilot study estimates, we plan to recruit 160 participants, i.e., 80 participants in each of the randomly assigned treatment groups for the baseline visits. Assuming an attrition rate of 20% at the follow-up visits, we will have 128 participants (64 in the OT and 64 in the P group) at the 4-week post-intervention follow-up visits. This sample size yields a power over 0.80, even based on a very conservative Bonferroni correction for multiple comparisons (i.e., testing twelve hypotheses), which lowers the alpha level from $\alpha=0.05$ to $\alpha=0.006$. However, our proposed data-analytic strategy will use the Benjamini and Hochberg procedure to control for multiple comparisons, which is less stringent than the Bonferroni correction, and thus we expect the actual power to be larger than 0.80.

Hypotheses and data-analytic strategy: We summarize all hypotheses and planned analyses in **Table 3 for aims 1 and 2.** The statistical analyses will be conducted by Co-I [name] (Biostatistician) in

Protocol: IRB201801467 (UCOPE Study)

IRB version: 10/1/2018

PI version: 05/10/2024

collaboration with [name] (Consultant, Institute on Aging Biostatistics and Bioinformatics Core Leader, see letter of support) using R software. For studying the relationship between pre- to post-intervention (longitudinal) outcomes and predictors, we will fit linear mixed effects models (**LMEMs**) [1] with subject specific random effects to account for the within-subject correlation, by R function “lmer”.¹⁰⁹ Baseline outcomes and covariates will be adjusted to take account for confounding effects. Below is the formula for the linear mixed effect model:

$$y_{ik} = \mu + \alpha_i + \beta \mathbb{I}(z_i = 1) + \sum_{l=0}^L \gamma_l x_{il} + \eta \mathbb{I}(k = 2) + \theta \mathbb{I}(z_i = 1, k = 2) + \varepsilon_{ik}, \alpha_i \sim N(0, \sigma_0^2), \varepsilon_{ik} \sim N(0, \sigma^2) \quad [1]$$

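### The 20% limit on LCModel %SD is relative to the estimated concentration, so if fits lie near the limit it can bias a true oxytocin effect on MI, Cho and tCr towards zero

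*Combined protocol and SAP*

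**What the plan says.** Section 6, Magnetic Resonance Spectroscopy (MRS), names the metabolites that LCModel will quantify: "OFF spectra will be analyzed using LCModel to give concentrations for additional metabolites NAA, Glx, Cho, MI, and Cr". Their concentrations "will be accepted with an LCModel Cramer-Rao lower bounds (%SD) of less than 20" percent, and the plan describes a value that passes as "a reliable estimate for a given metabolite for group comparisons".

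Three of these metabolites carry Aim 2. H2b in Section 5 predicts a "decrease in brain metabolite concentrations associated with inflammation", naming MI, Cr and Cho. The data-analytic strategy states that "the primary outcomes are proton MRS metabolites in frontal brain regions (tCr, MI, Cho"), alongside the plasma immune markers. Table 3 assigns H2b to a linear mixed model comparing OT with placebo. On missing values the plan says only that "LMEMs allow for missing data if missing-at-random (MAR").

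For these metabolites the documents give no expected %SD, rejection rate, standard deviation or OT effect. They set no criterion based on absolute bound, signal-to-noise or linewidth, and plan no analysis that retains rejected fits.

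**The concern.** A quality filter should depend on the quality of the spectrum. This one also depends on the outcome, because the estimated concentration is the denominator of %SD. Two spectra with the same noise and the same absolute bound can be treated differently only because one concentration is lower.

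H2b predicts lower concentrations under OT. If that is true and a metabolite is fitted with %SD near 20%, the OT phase can lose more values than the placebo phase, and the values lost are its lowest. Whether a value is missing then depends on the value that was discarded, which the missing-at-random condition for the mixed model does not cover. The kept OT values are shifted upwards more than the kept placebo values, so the estimated OT effect on an Aim 2 primary outcome is too small.

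**Working it through.** The plan states no figure on this point, so there is nothing to reproduce.

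**Inputs from the documents.** The 20% limit (MRS section); the direction of H2b (Section 5); the mixed model (Table 3); and the planned follow-up sample: "Assuming an attrition rate of 20% at the follow-up visits, we will have 128 participants", which is 160 × 0.80 = 128.

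**Inputs assumed.** Placebo mean 1.0; OT mean 0.90 (a 10% drop); between-person CV 15%; within-person CV 5%; fit noise with SD equal to the absolute bound. 'Typical %SD' is the absolute bound as a percentage of the placebo mean, and is varied.

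**Step 1: what the rule does.** Keep if bound / estimate < 0.20, that is, if estimate > 5 × bound. For a bound of 0.19, an estimate of 1.00 gives 19% and is kept; an estimate of 0.90 gives 0.19 / 0.90 = 21.1% and is rejected.

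**Step 2: rejection by phase, same bound for everyone.** The SD of an estimate is √(0.15² + 0.05² + bound²), and the cut-off is 5 × bound.

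| Typical %SD | Cut-off | SD | Placebo rejected | OT rejected |
|---|---|---|---|---|
| 12% | 0.60 | 0.198 | P(z < -2.02) = 2% | P(z < -1.51) = 6.5% |
| 15% | 0.75 | 0.218 | P(z < -1.15) = 13% | P(z < -0.69) = 25% |
| 18% | 0.90 | 0.240 | P(z < -0.42) = 34% | P(z < 0) = 50% |

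**Step 3: what this does to the means, at 15%.** The mean of a normal variable truncated from below is μ + SD × φ(z) / (1 - Φ(z)). Placebo: 1.00 + 0.218 × 0.207 / 0.874 = 1.052. OT: 0.90 + 0.218 × 0.315 / 0.754 = 0.991. The difference in kept values is about 0.061 instead of 0.100, a loss of about 39% when all accepted values are compared.

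**Step 4: complete pairs.** A crossover comparison within persons loses less. Simulated crossover pairs gave these losses of the OT effect:

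| Absolute bound | OT effect | 12% | 15% | 18% |
|---|---|---|---|---|
| Same for all | Additive | 7% | 23% | 42% |
| Same for all | Proportional | 4% | 17% | 35% |
| Varies by session (log-SD 0.3) | Proportional | about 4% | about 5-7% | about 8% |

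A session-varying bound with larger losses gave 14% at a typical %SD of 15%. At a typical %SD of 8% or less, no setting lost more than 1.6% on pairs or 4% on all accepted values.

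**Step 5: a mixed model.** A random-intercept model was fitted to simulated two-period data: 128 people, CV 15%, within-person correlation 0.6, bound varying with log-SD 0.3, 10% OT drop, 60 replicates. Losses were 0.0% at a typical %SD of 5%, 3.7% at 10%, 7.6% at 15% and 11.9% at 18%. At 15%, for example, the estimate moved from -0.0984 with all fits kept to -0.0909 after filtering: 1 - 0.0909 / 0.0984 = 7.6%.

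**Step 6: no OT effect.** With the OT effect set to zero, the two phases lost values at about the same rate (20.0% and 20.1% at a typical %SD of 15%), and the filtered estimate stayed near zero (0.0009).

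**The case against.** The strongest objection is that the problem may never arise. The rule acts only on fits near 20%, and nothing in the documents shows that MI, Cho or tCr will be fitted that poorly. At a typical %SD of 5% the filter rejects almost nothing. A reader might infer that the rule will remove OT-phase data and will shrink the OT effect. The documents do not support that: it needs both a true OT decrease and fits near the limit, and neither is established. Placebo-phase and baseline values are rejected too; the bias comes only from the difference in rejection.

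The largest losses also come from an extreme case in which everyone has the same absolute bound, so that concentration has most influence on rejection. Bounds that vary between sessions reduce the loss, and the mixed-model losses are at the lower end. This stands, and it is why a range is given.

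A reader might also infer that H2c, which relates falls in metabolites to falls in pain, loses the people with the largest falls. That does not follow. The rule screens the level, not the change, so someone who starts high can fall a long way and still be kept.

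Finally, the rule cannot manufacture an OT effect, because there is no bias when OT does nothing. That is correct and limits the harm to lost sensitivity and an underestimated effect.

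What remains is the mechanism and its direction. Where the rule has any effect, it selects on the outcome, against the hypothesis, in a way that the missing-data assumption does not cover.

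**Conclusion.** The point holds in conditional form. At equal spectral quality the relative limit rejects low concentrations first. If OT lowers MI, Cho or tCr and fits lie near 20%, it can cause outcome-dependent missingness that biases H2b towards no effect.

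The size cannot be judged from the documents. Under the assumptions above, the bias is negligible for well-fitted metabolites (typical %SD of 8% or less) and grows to a material share of the effect between 12% and 18%. Where it falls within the range depends on how much the bound varies between sessions, whether the OT effect is additive or proportional, and which analysis is used. The false-positive risk for H2b is not raised.

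**What to change.** Amend the MRS acceptance rule and the analysis text as follows.

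1. Compute the absolute bound for each fit as %SD × estimate / 100. Apply the 20% limit to that bound divided by the mean of the metabolite pooled over all participants and phases, calculated blind to treatment. Keep low estimates from spectra that meet this limit.
2. Report the number of rejected values by metabolite and by phase (baseline and post-intervention, OT and placebo).
3. Add a sensitivity analysis of H2b that keeps all fits.

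The cost is a few sentences: %SD and the estimate are both in the LCModel output, and no new data are needed. Some low, relatively noisier values stay in. In the simulations the absolute limit returned -9.9% to -10.1% for a true -10%. That result is largely built in, because the simulated bound did not depend on concentration; items 2 and 3 are the check on real data. Where fits are good, the change alters almost nothing.
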